3.2.2 Secondary Outcome Measures

Secondary outcomes will include 30-day all cause readmissions (for those patients who have an index hospitalization), emergency room visits, cardiovascular events and deaths, and disease-specific hospitalizations for cardiovascular complications, congestive heart failure, volume overload, accelerated/malignant/uncontrolled hypertension, acute coronary syndromes, myocardial infarction, stroke, coronary/peripheral revascularization, limb ischemia/amputations, diabetes complications, uncontrolled diabetes, hypoglycemia, acute kidney injury, hyperkalemia, electrolyte disturbances, medication errors, drug toxicity, and infections. For those patients who are hospitalized all readmissions within 30 days of the index hospitalization will be captured from the electronic health records of the participating healthcare sites, Dallas Fort Worth Hospital Council or ACO database (for ProHealth, Connecticut) and VA of North Texas. Emergency room visits will be similarly captured from the electronic health records, DFW Hospital Council, ProHealth database and VA database.

Cardiovascular events include congestive heart failure, acute coronary syndromes, myocardial infarction, coronary and peripheral revascularization, stroke and limb ischemia/amputation. Deaths from any cause will be captured. Deaths will be classified as cardiovascular or non-cardiac related. Deaths will be captured from the electronic health records of the participating healthcare systems as well as from the Dallas Fort Worth Hospital Council and ACO database (for ProHealth, Connecticut), and VA EHR. We will also verify if enrolled patients who do not have an encounter in our systems within two year of study participation are classified as dead or alive using the Social Security Index.

Other secondary outcomes captured in the study from the electronic health records will include descriptive patient characteristics for patients with a triad of CKD, diabetes and hypertension including demographic data, information of patient comorbidities clinical data, medications, laboratories, and procedures, and changes in renal function (eGFR) and episodes of acute kidney injury as well as safety/adverse events. We will use the wealth of information available in the EHR to advance disease-specific phenotyping of our patient population.^[72] Resource utilization will also be measured capturing not only hospitalization but also clinic visits and procedures (diagnostic and therapeutic).

As previously noted, Patient Reported Outcomes will not be captured initially but will be addressed as part of a future proposal in the study. Patient Reported Outcomes (PROs) are assessments directly reported by patients without interpretations by others and are increasingly recognized as key and valuable components of clinical trials^[87]. A PRO survey derived for core domains and corresponding measures by the PCOR Net Reported Outcomes Common Measures Working Group (CMWG) will be used to measure health related quality of life and physical and emotional well-being of patients. Primary care practitioner reported outcomes and satisfaction with resources and ability to manage patients with coexistent CKD, diabetes and hypertension will be measured with a survey adapted from collaborative disease management initially developed for late-life depression in primary care^[88].

4. Study Design

The study will employ a prospective stratified cluster randomization design. The stratum is each of the four large healthcare systems participating in the study. The unit of randomization will be primary care practices. In some healthcare systems (Parkland and North Texas VA) primary care practices are defined by an individual primary care practitioner caring for a unique group of patients with a permanently designated team of one RN and one medical assistant with no overlap with the practices of other primary care practitioners. In other healthcare systems (THR and ProHealth) clinical practices are defined as group of patients cared by practitioners sharing personnel and workflows in the same physical location and randomized as a single unit. The cluster design of the study is best suited to detect important differences in outcomes between the intervention and control groups^[8,55]. The decision to use primary care practices as a unit for randomization in the study is based on the ability to implement different models of care in the active intervention sites as compared to the control sites. The collaborative model of care which includes novel information technology, subject identification, facilitation of patient care, monitoring of outcomes and participation from facilitators can be most efficiently applied to the workflow of practices when they are fully randomized to active intervention. The cluster randomization design with practices receiving collaborative primary care-subspecialty care versus standard care also limits the risk of cross-contamination between intervention and control groups in the study.

Primary care practices will be stratified by healthcare systems and randomly allocated to either intervention group or standard medical care group using a randomized permutation block within stratum. Based on the assignment of the practice where a patient receives medical care each patient will be assigned either to the intervention group or the standard medical care group.

All eligible patients of practices who are randomized to the study will be included in the comparison of the two intervention groups regardless of intervention compliance (intention-to-treat analysis) to investigate if patients in intervention group have significantly less all-cause hospitalizations than those in the standard medical care group. Evaluation will also be performed to determine treatment effects on disease-specific hospitalizations, ER visits, cardiovascular events and deaths.

There will be two study groups: active intervention group randomized to the collaborative model of care facilitated by novel information technology and practice facilitators and standard/usual care group.

The total number of patients to be studied is 10,991. (see *study table 4*)

Healthcare System	Number of Practices	Number Patients to be Enrolled
Parkland Healthcare Systems	25	3,367
Texas Health Resources	40	3,610
ProHealth Connecticut	50	3,181
North Texas VA	9	833

Table 4
Study recruitment will occur over a period of two years. The expected duration of subject participation is 12 months.

The intervention in the active group is implementation of a collaborative model of care that facilitates delivering best care practices to patients who have coexistent CKD, type 2 diabetes and hypertension. The model uses a novel information technology platform and practice facilitators with the purpose of allowing for early identification of patients with objective criteria and to implement best practices of care, monitor important clinical measures, adjust treatments and achieve improved outcomes. The intervention will be delivered in the outpatient setting.

The primary outcome measured during the trial is 12-month all-cause hospitalization rate for all the study participants. Secondary outcomes measured during the trial include 30-day disease-specific readmissions (for all patients with an index hospitalization), emergency room visits, cardiovascular event, deaths and disease-specific hospitalizations.

Other secondary outcomes measured in the study include adverse safety events, episodes of acute kidney injury and changes in estimated GFR.

Data collection for assessment of study objectives will be mainly based on information technology tools to capture data from the electronic health record. Some data fields will require collection of data from Dallas Fort Worth Regional Hospital Council, ProHealth ACO databases, VA of North Texas and Social Security Death Files Index.

There will be an interim analysis for efficacy of the intervention when 50% of the primary outcome data is available. This the consensus recommendation after review of the protocol and incorporating input from NIH, DSMB and OHRP. The study biostatisticians will review trends quarterly including patient volumes compared to goals from power calculations and inform study team and DSMB of any concerns based on trends of findings.

A DSMB (Data Safety Monitoring Board) has been assembled by the NIDDK and will oversee study planning and implementation of the study.

5. Selection and Enrollment of Participants

The total sample size of patients with the triad of CKD, type 2 diabetes and hypertension among participating sites in the four large healthcare systems in our study exceeds 28,118. The actual number of patients to be studied is 10,991.

The study will include patients 18-85 years old with CKD, diabetes and hypertension. Men, women, and minorities will participate in the study. Children will not participate as this study is focused on adults with multiple chronic conditions.

The outpatient population to be studied will be drawn from four large healthcare systems participating in the study. Parkland Health and Hospital System is the safety-net health system for Dallas County. Texas Health Resources is a large private, non-profit healthcare system network in North Texas. The North Texas Veterans Administration Healthcare System provides care for US veterans. ProHealth Physicians is Connecticut's largest network of primary care physicians.

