Secondary outcomes captured in the study will include 30-day all cause readmissions (for those patients who have an index hospitalization), emergency room visits, cardiovascular events and deaths, and disease-specific hospitalizations for cardiovascular complications, congestive heart failure, volume overload, hypertension complications, acute coronary syndrome, myocardial infarction, coronary/peripheral revascularization, stroke, amputation/limb ischemia, uncontrolled diabetes, hypoglycemia, diabetes complications, acute kidney injury, hyperkalemia, electrolyte disturbances, medication errors, drug toxicity and infections.. Data for secondary outcomes will be obtained as outlined above with the primary outcomes. In addition, we will verify if enrolled patients who do not have an encounter in our systems within two years of study participation are classified as dead or alive using the Social Security Index.

Other secondary outcomes captured from the electronic health records will include descriptive patient characteristics including demographic and clinical data from patients with CKD, diabetes and hypertension as well as information on patient comorbidities, changes in renal function (eGFR), episodes of acute kidney injury as well as safety/adverse events. Resource utilization will be captured from careful evaluation of hospitalization events, clinic visits and diagnostic and therapeutic procedures completed.

Interventions and Duration

Figure: Schematic Design ICD-Pieces Trial summarizes main components of the study

Schematic Design ICD-Pieces Trial

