7.3 Follow up Visits

Measures of blood pressure, blood glucose, kidney function (creatinine, eGFR), lipid levels, urine protein/urine albumin as well as pre-specified safety events will be captured from electronic health records at the time of patient contacts with the healthcare system for scheduled or unexpected visits for patients. Information will be then directed to primary care teams per study protocol.

Main study outcomes will be captured throughout the study for both intervention and control groups using the same tools in the electronic health record and access to DFW Regional Hospital Council, ProHealth database and VA electronic information systems.

The study does not specify the frequency of visits for study participants. It is anticipated that patients with the triad of CKD, diabetes and hypertension will usually be seen at a minimum of every 3-6months in most participating clinics.

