15.1 Data Collection

Data capture will be aggregated on a central cloud based (Software-as-a Service) SaaS platform hosting the Pieces™ software. Flat file transfer via SFTP will occur and HL7 based data integration will occur with a site specific selection of the best method to transmit data centrally. In the instance that external approval of data transfer cannot occur, a process of locally matching patient selection criteria on software server with a local firewall will be implemented with a process to allow deidentified data to the SaaS server will be implemented. Access to the central server will be restricted using Secure VPN tunnel with two factor authorization. The Secure Cloud Hosting Environment will be FISMA (**Federal Information Security Management Act of 2002**) compliant.

Hospitalization and Death Outcome Data:

Data requests by the National Association for Public Health Statistics and Information Systems (NAPHSIS) Death index information from the CDC will be obtained after completion of IRB submission for approval and then performed at the termination of the study a single time to obtain death outcomes after enrollment and follow up of planned time period for augmentation of EHR stored death date and death status of inpatient discharge to ascertain mortality outcomes.

Master Patient Index matching to a shared Dallas Fort Worth Hospital Council data set will occur for the THR and PHHS site using the REMPI match system to obtain inpatient hospitalization events throughout the Dallas-Fort Worth area. Patient outcomes within the outside of the Veterans Affairs System will occur with an additional research effort to assess the

feasibility of patient patching between the Veterans Affairs patient index and the DFWHC data to provide additional hospitalization events for veterans outside the VHANTX system.

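### The plan states two different death-index checks without saying which governs the death outcome; the one in the outcome definition depends on encounters after randomisation and should be replaced by linkage of every enrolled patient

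*Combined protocol and SAP*

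**What the plan says.** Section 3.2.2 takes deaths from the health records of the participating systems, the Dallas Fort Worth Hospital Council, the ACO database and the VA record. It adds a Social Security Index check on whether "enrolled patients who do not have an encounter in our systems within two year of study participation are classified as dead or alive". The Protocol Summary (Design and Outcomes) applies the same check to "enrolled patients who do not have an encounter in our systems within two years of study participation".

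Section 15.1 describes a request for death index data obtained through a national vital-statistics association and the CDC. It is to be "performed at the termination of the study a single time to obtain death outcomes after enrollment and follow up of planned time period", and its purpose is "for augmentation of EHR stored death date and death status of inpatient discharge to ascertain mortality outcomes". No encounter condition is attached, but the text does not say that all enrolled patients are submitted.

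Sections 4 and 9.3 also name Social Security death files as a source, without any encounter condition. Section 9.3 accepts that some deaths may come to light only through those files.

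On visits, Section 7.3 sets no schedule but expects that patients "will usually be seen at a minimum of every 3-6months in most participating clinics". On cause, Section 3.2.2 says: "Deaths will be classified as cardiovascular or non-cardiac related".

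**The concern.** Encounters happen after randomisation and may be affected by the intervention. A rule that sends patients to a death index according to whether they had an encounter therefore makes detection of the outcome depend on something the treatment can change. The trigger also fits the trial poorly: follow-up is 12 months, the window is two years, and most patients are expected back within 3 to 6 months. Someone seen at month 3 who dies at home in month 7 has had an encounter and, on one natural reading, is never looked up.

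Death is a secondary efficacy outcome (3.2.2), a serious adverse event (9.2.3) and an endpoint of the frailty Cox models (11.3). The index matters most for out-of-hospital deaths because the routine sources lean towards inpatient data: the Hospital Council match in Section 15.1 obtains inpatient events for two of the systems, and matching for veterans is still a feasibility question.

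Two teams following different sections could arrive at different death counts from the same patients.

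**Working it through.** **No plan figure for deaths.** The documents give no death rate, no power for death, no share of deaths outside the records and no visit rates by arm. Their one size figure, 10,991, is for hospitalization (Section 11.2). It reproduces: 1,907 per arm for 14% versus 11% at two-sided 5% and 80% power, times a patient-weighted mean design effect of 2.8814 (ICC 0.015; 176.8, 118.5, 83.5 and 121.4 available patients per clinic), gives 2 × 1,907 × 2.8814 ≈ 10,990. Death data do not enter it.

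**The rules side by side.**

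| Place | Source | Who is checked | When |
|---|---|---|---|
| Protocol Summary; 3.2.2 | Social Security Index | Enrolled patients with no encounter within two years of participation | Not stated |
| 15.1 | A different death index | No restriction stated; all patients not expressly included | Once, at study termination |
| 4; 9.3 | Social Security death files | No restriction stated | Not stated |

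The entries differ in source, in population or in both, and no section ranks them.

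**What the two-year phrase can mean.** Take the patient seen at month 3 who dies at home in month 7.

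1. Any encounter after enrolment counts. The month-3 visit disqualifies the patient and no check is made.
2. The enrolment visit counts too. Section 7.2 starts the study at a clinic visit, so almost nobody in either arm qualifies, and detection does not vary with visit frequency.
3. The clock runs from the last encounter or from the end of participation. The patient is checked, but late. With two years of recruitment and 12 months of follow-up, the last patient's month 12 falls at calendar month 24 + 12 = 36. A last enrollee seen at month 3 would become checkable at 24 + 3 + 24 = 51, which is 15 months later.

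**Size under reading 1, on assumptions.** Assume that deaths are uniform over 12 months and that the first return visit is at month 3 or month 6, the ends of the range in Section 7.3. The share of first-year deaths after a return visit is s = 1 − 3/12 = 0.75 or s = 1 − 6/12 = 0.50. Let f be the share of deaths absent from all routine sources, unrelated to timing. The share of deaths lost is f × s. For an assumed f of 0.2 to 0.4, this runs from 0.2 × 0.50 = 0.10 to 0.4 × 0.75 = 0.30. The documents supply no f, so this shows the mechanism and is not an estimate. If the Section 15.1 request covers everyone and its index is complete, the loss is 0.

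**Difference by arm.** With equal true mortality, the observed risk ratio is (1 − f₁s₁)/(1 − f₀s₀), with 1 for intervention and 0 for control. Equal f and equal s give 1.00. Equal f with earlier returns in the intervention arm gives a value below 1. But f need not be equal: f₁ = 0.2, s₁ = 0.75 and f₀ = 0.3, s₀ = 0.50 give 0.85/0.85 = 1.00. The sign is therefore undetermined.

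**The case against.** The strongest reply is that the plan already contains the remedy. Section 15.1 schedules a death index request without an encounter condition, Sections 4 and 9.3 name Social Security death files without one, and 3.2.2 presents its check as an addition to four other sources. On that view the restricted check is a harmless extra. Much of this stands. A reader might infer from 3.2.2 alone that no other patient is ever sent to an index, or that deaths after a clinic visit will be lost; the documents as a whole do not support either. What remains is that the outcome definition states the restricted rule in two places, nothing says that Section 15.1 overrides it, and Section 15.1 is silent on whether everyone is submitted.

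A second reply is that the two-year phrase has a reading under which the month-7 death is checked. That is correct. It leaves the rule ambiguous and, on that reading, late.

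A reader might also infer a bias in favour of the intervention. Section 6.7 calls higher utilization possible, and Appendix I schedules repeat nurse visits after drug changes, so more frequent contact is plausible. But activating the protocols is optional, no visit rates by arm are given, and the 12 months of monitoring of intervention patients in Section 9.4 could improve death capture in that arm.

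Finally, a reader might think that missed deaths distort the primary comparison. Sections 11.2 and 11.3 compare one-year hospitalization rates and nowhere remove or censor patients who die, so a detected death without hospitalization would stay in the denominator just as an undetected one would.

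**Conclusion.** The concern holds as an unresolved inconsistency in how a secondary efficacy and safety outcome is ascertained. The Protocol Summary and Section 3.2.2 state an encounter-dependent check; Section 15.1 states a single end-of-study request to a different index without that condition; the governing rule and the coverage of the second are not given. Loss of out-of-hospital deaths follows if the first rule governs and any encounter after enrolment counts. Its size is then f × s with f unknown, and it is zero if the Section 15.1 request is complete and covers all patients. A difference between arms is possible, with neither magnitude nor direction established. The primary comparison as planned and the sample size are not affected. It is worth correcting because the fix is specific and nearly free.

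The cause classes are a minor wording point. Section 3.2.2 lists stroke among cardiovascular events, so a stroke death can be both cardiovascular and non-cardiac. Section 11.3 names no cause-specific mortality analysis, so little depends on this.

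**What to change.** - In the Protocol Summary and Section 3.2.2, delete the condition that the patient had no encounter within two years.
- In Sections 3.2.2 and 15.1, name one death index and state that every enrolled patient in both arms, except those who opted out of data use, is linked to it once, after the last patient's month 12 and regardless of encounters. Count deaths dated within 12 months of each patient's own start.
- Align the mentions of death files in Sections 4 and 9.3 with that rule.
- Make the cause classes exclusive: cardiovascular (including stroke), non-cardiovascular, and unknown. Confirm whether the chosen index supplies cause of death, which Section 15.1 does not say.

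The cost is protocol wording and possibly a longer list of patients submitted. The single request is already planned, and Section 15.2 already foresees using the protected ProHealth identifiers for final outcome linkage. Enrolment and sample size do not change.

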5.1 Subject Inclusion Criteria

In order to participate in the study, patients should be 18-85 years of age and have coexistent CKD, type 2 diabetes and hypertension.

5.1.1 CKD Inclusion Criteria (present at least \geq 3 months apart) ^[12,5,86]

1. There will be two or more eGFRs less than 60ml/minute or
2. Two or more positive tests for albuminuria and/or proteinuria

Albuminuria/proteinuria can be defined by quantitative criteria with albumin/creatinine ratio greater than 30, urine protein creatinine ratio greater than 200 or positive dipstick with protein detection (adjusted for urinary concentration/specific gravity). ^[12,5,86]

Figure 5.1.1 summarizes identification of CKD candidate pool

